**In Mayo Clinic Subjects Only:**

## 9.2.2.4 Patient Derived Xenografts (PDX)

To generate individual patient derived xenografts (PDX), 2 additional research core specimens will be obtained during the baseline (pre-treatment) and progression of disease (PD) biopsies. The fresh tumor tissue will be immediately injected into 3 immunodeficient *scid* mice for the creation of human tissue xenografts (per IACUC A18014). The xenograft tumor samples will be used to evaluate mechanisms of de novo and acquired resistance to alisertib. These PDX models will be also be used for future research purposes, such as testing novel compounds and different regimens. All the tumor tissues from xenografts will be stored in the [REDACTED]

**10. SPECIMEN BANKING**

Any leftover study blood and tissue samples may be stored for future research studies. The subjects will consent to the future use of samples in the consent form for the study. Any samples will only be released for use in future studies after approval by the TBCRC and other regulatory bodies, as appropriate.

The study PI and collaborators have approval by the TBCRC to use all research bio-specimens collected during the conduct of this trial to address the research questions described in the protocol document. All future use of residual or repository specimens collected in this trial for purposes not prospectively defined will require review and approval by the TBCRC according to its established policies, whether the specimens are stored in a central site or at a local institution in a virtual repository.

Secondary use of bio-specimens for new endpoints must be submitted to the TBCRC Central Office for possible review by the TBCRC Correlative Science Review Committee.

## 11. STUDY CALENDAR

### 11.1 Test Schedule for Arm 1: Alisertib

		Pre-registration period (spans the first 28 days after pre-registration) 	Alisertib Treatment Phase		For patients who meet requirements set out in Section 6.1.2 Alisertib + Fulvestrant Treatment Phase	
			Day 1 of each treatment cycle* 	At PD or discontinuation of alisertib	Day 1 of each treatment cycle 	At PD or discontinuation of alisertib + fulvestrant
Tests and procedures	≤28 days prior to Pre-registration					
History and exam, wt, PS	X		X 	X	X	X
Adverse event assessment		X 	X 	X	X	X
Height	X					
Follicle-stimulating hormone (FSH) level 		X				
Hematology group – Hemoglobin – White blood cell count – Absolute neutrophil count – Platelets		X	X 	X	X 	X

 For crossover registration procedure, see Section 5.4

 Hematology and chemistry blood tests and adverse event assessment for registration must be done ≤21 days prior to registration

 Labs, scans, tests and observations may be obtained ≤4 days prior to Day 1 of each cycle.

 Labs, H&E, wt, PS and AE assessment completed prior to switch to the combination of fulvestrant and alisertib may be used for Day 1 of “new” Cycle 1 tests if obtained ≤14 days prior to start of combination treatment.

 For Cycle 1, Day 1, nurse assessment may replace “History and exam, wt and PS” IF most recent physician/provider exam is ≤14 days prior to C1D1.

 Baseline AE assessment is to be performed anytime in the window of ≤4 days prior to registration. AE assessment need not be repeated Cycle 1 Day 1.

 For women <60 years of age with amenorrhea for >12 months

 Hematologic parameters will be assessed on Cycle 1 Day 15 (±1 day) after the patient has taken their morning dose of alisertib

 Hematologic parameters will be assessed on Day 15 (±1 day) of first cycle in the crossover phase any time after the patient has taken their morning dose of alisertib prior to the administration of the loading dose of fulvestrant.

		Pre-registration period (spans the first 28 days after pre-registration) 	Alisertib Treatment Phase		For patients who meet requirements set out in Section 6.1.2  Alisertib + Fulvestrant Treatment Phase	
			Day 1 of each treatment cycle* 	At PD or discontinuation of alisertib	Day 1 of each treatment cycle 	At PD or discontinuation of alisertib + fulvestrant
Tests and procedures	≤28 days prior to Pre-registration					
Chemistry group – Sodium – Potassium – BUN – Creatinine – Calcium – Glucose – Albumin – AST – ALT  – Alkaline Phosphatase – Total Bilirubin 		X	X	X	X	X
Tumor measurement 	X		X	X	X 	X
Alisertib			X		X	
Fulvestrant					X 	
Patient Medication Diary (Appendix III) 			X	X	X	X

 FOR CYCLE 1 DAY 1 ONLY: If either to the following holds: (1) total bilirubin >1.5 x ULN or (2) Alanine transaminase >5 x ULN, then the patient should not begin protocol treatment. The patient should go off study and will be considered a cancel (see Section 6.4.8).

 The same imaging modality (CT scan, CT component of a PET/CT, or MRI) must be used throughout the study. Baseline imaging should be obtained ≤28 days prior to Registration. Tumor measurements are to be done at the completion of Cycles 2, 4, 6, etc., for first two years or until disease progression, whichever is first. Patients who have achieved complete response, partial response, or stable disease for ≥2 years may reduce imaging to every fourth cycle.

 Scans are not required Day 1 of Cycle 1 of fulvestrant and alisertib. The scans taken at the time of progression on alisertib will serve as the baseline scan for the fulvestrant and alisertib treatment phase of the study.

 Fulvestrant will be given on Day 1 of every cycle and on Day 15 (±1 day) of Cycle 1 only.

 The diary must begin the day the patient starts taking the medication and must be completed per protocol and returned to the treating institution at the completion of each cycle of treatment (approximately every 28 days). Compliance must be documented in the medical record by any member of the care team.

			Alisertib Treatment Phase		For patients who meet requirements set out in Section 6.1.2 Alisertib + Fulvestrant Treatment Phase	
Tests and procedures	≤28 days prior to Pre-registration	Pre-registration period (spans the first 28 days after pre-registration) 	Day 1 of each treatment cycle* 	At PD or discontinuation of alisertib	Day 1 of each treatment cycle 	At PD or discontinuation of alisertib + fulvestrant
Mandatory tumor tissue specimens for research (see Section 9.0)		X 	X 	X 	X	X 
Research Correlative blood studies (collection for CTCs and cf-DNA)		X	X 	X	X 	X

\* Cycle length is 28 days ±3 days

 The pre-registration biopsy will be utilized for central ER evaluation and correlative studies.

 Performed once up to 4 days prior to the start of Cycle 2. Must be performed prior to initiation of treatment for Cycle 2.

 Performed once up to 14 days after progressive disease is identified. Must be performed prior to initiation of next therapy, which may be the combination of fulvestrant and alisertib for those eligible and electing to crossover, or may be standard therapy for those who elect to come off study or are not eligible for cross-over. If a lung lesion is the only site of disease amenable to a biopsy, then this biopsy will not be mandatory (except for patients with ER <10% or ER negative on the pre-registration biopsy who are desiring and eligible for cross-over).

 Biopsy at PD after crossover is optional, except for patients with a lung lesion as the only site of disease amenable to biopsy in which case the biopsy at PD after crossover is not allowed.

 At the end of Cycle 1, prior to treatment initiation on Day 1 of Cycle 2 (only). May be drawn with clinical labs ≤4 days prior to C2D1.

 At the end of the first cycle of combination therapy, prior to treatment initiation on Day 1 of the second cycle of combination therapy (only).

## 11.2 Test Schedule for Arm 2: Alisertib + Fulvestrant

Tests and procedures	≤28 days prior to Pre-registration	Pre-registration period spans the first 28 days after pre-registration 	Day 1 of each treatment cycle 22*	At PD or discontinuation of therapy
History and exam, wt, PS	X		X 	X
Adverse event assessment		X	X 	X
Height	X			
Follicle-stimulating hormone (FSH) level 		X		
Hematology group				
– Hemoglobin				
– White blood cell count		X	X 	X
– Absolute Neutrophil count				
– Platelets				
Chemistry group				
– Sodium				
– Potassium				
– BUN				
– Creatinine				
– Calcium		X	X	X
– Glucose				
– Albumin				
– AST and ALT 				
– Alkaline Phosphatase				

 Hematology and chemistry blood tests and adverse event assessment for registration must be done ≤21 days prior to registration.

 Labs, scans, tests and observations may be obtained ≤4 days prior to Day 1 of each cycle.

 For Cycle 1, Day 1, nurse assessment may replace “History and exam, wt and PS” IF most recent physician/provider exam is ≤14 days prior to C1D1.

 Baseline AE assessment is to be performed anytime in the window of ≤4 days prior to registration. Adverse event assessment need not be repeated prior to Cycle 1, Day 1.

 For women <60 years of age with amenorrhea for >12 months.

 Hematologic parameters will be assessed on Day 15 of Cycle 1 any time after the patient has taken their morning dose of alisertib but before administration of fulvestrant.

 FOR CYCLE 1 DAY 1 ONLY: If either to the following holds: (1) total bilirubin >1.5 x ULN or (2) alanine transaminase >5 x ULN, then the patient should not begin protocol treatment. The patient should go off study and will be considered a cancel (see Section 6.4.8).

Tests and procedures	≤28 days prior to Pre-registration	Pre-registration period spans the first 28 days after pre-registration 	Day 1 of each treatment cycle 22*	At PD or discontinuation of therapy
– Total Bilirubin 				
Tumor measurement 	X		X	X
Alisertib			X	
Fulvestrant			X 	
Patient Medication Diary (Appendix III) 			X	X
Mandatory tumor tissue specimens for research (see Section 9)		X 	X 	X 
Correlative blood studies (collection for CTCs and cf-DNA)		X	X 	X

\* Cycle length is 28 ±3 days

 The same imaging modality (CT scan, CT component of a PET/CT, or MRI) must be used throughout the study. Baseline imaging should be obtained ≤28 days prior to Registration. Tumor measurements are to be done at the completion of Cycles 2, 4, 6 etc., for first two years or until disease progression, whichever is first. Patients who have achieved complete response, partial response, or stable disease for ≥2 years may reduce imaging to every fourth cycle.

 Fulvestrant will be given on Day 1 of every cycle and on Day 15 of Cycle 1 only.

 The diary must begin the day the patient starts taking the medication and must be completed per protocol and returned to the treating institution at the completion of each cycle of treatment (approximately every 28 days). Compliance must be documented in the medical record by any member of the care team.

 The pre-registration biopsy will be utilized for central ER evaluation and correlative studies.

 Biopsy must be performed ≤4 days prior to initiation of Cycle 2 treatment

 Performed once up to 14 days after progressive disease is identified. Must be performed prior to initiation of next therapy. If a lung lesion is the only site of disease amenable to rebiopsy, then this biopsy will not be mandatory.

 At the end of Cycle 1, prior to treatment initiation on Day 1 of Cycle 2 (only). May be drawn with clinical labs ≤4 days prior to C2D1

## 12. MEASUREMENT OF EFFECT

For the purposes of this study, patients should be re-evaluated for response after every 2 cycles of treatment.

NOTE: Patients who have achieved complete response, partial response, or stable disease for  $\geq 2$  years may reduce imaging to every fourth cycle.

Response and progression will be evaluated in this study using the international criteria proposed by the revised Response Evaluation Criteria in Solid Tumors (RECIST) Committee (version 1.1).(62) Changes in only the largest diameter (unidimensional measurement) of the tumor lesions are used in the RECIST criteria.

### 12.1 Definitions

Evaluable for toxicity: All patients will be evaluable for toxicity from the time of their first treatment with alisertib.

### 12.2 Disease Parameters

#### 12.2.1 Measurable

12.2.1.1 A non-nodal lesion is considered measurable if its longest diameter can be accurately measured as  $\geq 2.0$  cm with chest x-ray, or as  $\geq 1.0$  cm with CT scan, CT component of a PET/CT, or MRI.

12.2.1.2 A superficial non-nodal lesion is measurable if its longest diameter is  $\geq 1.0$  cm in diameter as assessed using calipers (e.g. skin nodules) or imaging. In the case of skin lesions, documentation by color photography, including a ruler to estimate the size of the lesion, is recommended.

12.2.1.3 A malignant lymph node is considered measurable if its short axis is  $\geq 1.5$  cm when assessed by CT scan (CT scan slice thickness recommended to be no greater than 5 mm).

NOTE: Tumor lesions in a previously irradiated area are not considered measurable disease.

#### 12.2.2 Non-measurable

All other lesions (or sites of disease) are considered non-measurable disease, including pathological nodes (those with a short axis  $\geq 1.0$  to  $< 1.5$  cm). Bone lesions, leptomeningeal disease, ascites, pleural/pericardial effusions, lymphangitis cutis/pulmonis, inflammatory breast disease, and abdominal masses (not followed by CT or MRI), are considered as non-measurable as well.

**Note:** ‘Cystic lesions’ thought to represent cystic metastases can be considered as measurable lesions, if they meet the definition of measurability described above. However, if non-cystic lesions are present in the same patient, these are preferred for selection as target lesions. In addition, lymph

nodes that have a short axis  $<1.0$  cm are considered non-pathological (i.e., normal) and should not be recorded or followed.

### 12.2.3 Specifications by methods of measurements

#### 12.2.3.1 Measurement of lesions

- All measurements should be recorded in metric notation (i.e., decimal fractions of centimeters) using a ruler or calipers.
- The same method of assessment and the same technique must be used to characterize each identified and reported lesion at baseline and during follow-up. For patients having only lesions measuring at least 1 cm to less than 2 cm must use CT imaging for both pre- and post-treatment tumor assessments.

### 12.2.4 Method of assessment

- Conventional CT and MRI: This guideline has defined measurability of lesions on CT scan based on the assumption that CT slice thickness is 5 mm or less. If CT scans have slice thickness greater than 5 mm, the minimum size for a measurable lesion should be twice the slice thickness.
- As with CT, if an MRI is performed, the technical specifications of the scanning sequences used should be optimized for the evaluation of the type and site of disease. The lesions should be measured on the same pulse sequence. Ideally, the same type of scanner should be used and the image acquisition protocol should be followed as closely as possible to prior scans. Body scans should be performed with breath-hold scanning techniques, if possible.
- PET-CT: If the site can document that the CT performed as part of a PET-CT is of identical diagnostic quality to a diagnostic CT (with IV and oral contrast), then the CT portion of the PET-CT can be used for RECIST measurements and can be used interchangeably with conventional CT in accurately measuring cancer lesions over time.
- Chest X-ray: Lesions on chest x-ray are acceptable as measurable lesions when they are clearly defined and surrounded by aerated lung. However, CT scans are preferable.
- FDG-PET: FDG-PET scanning is allowed to complement CT scanning in assessment of progressive disease [PD] and particularly possible 'new' disease. A 'positive' FDG-PET scanned lesion is defined as one which is FDG avid with an uptake greater than twice that of the surrounding tissue on the attenuation corrected image; otherwise, an FDG-PET scanned lesion is considered 'negative.' New lesions on the basis of FDG-PET imaging can be identified according to the following algorithm:
  - a. Negative FDG-PET at baseline with a positive FDG-PET at follow-up is a sign of PD based on a new lesion.
  - b. No FDG-PET at baseline and a positive FDG-PET at follow-up:
    - i. If the positive FDG-PET at follow-up corresponds to a new site of disease confirmed by CT, this is PD.

- ii. If the positive FDG-PET at follow-up is not confirmed as a new site of disease on CT at the same evaluation, additional follow-up CT scans (i.e., additional follow-up scans at least 4 weeks later) are needed to determine if there is truly progression occurring at that site. In this situation, the date of PD will be the date of the initial abnormal PDG-PET scan.
- iii. If the positive FDG-PET at follow-up corresponds to a pre-existing site of disease on CT that is not progressing on the basis of the anatomic images, it is not classified as PD.

#### 12.2.5. Measurement at Follow-up Evaluation:

- The cytological confirmation of the neoplastic origin of any effusion that appears or worsens during treatment when the measurable tumor has met criteria for response or stable disease is mandatory to differentiate between response or stable disease (an effusion may be a side effect of the treatment) and progressive disease.
- Cytologic and histologic techniques can be used to differentiate between PR and CR in rare cases (e.g., residual lesions in tumor types such as germ cell tumors, where known residual benign tumors can remain.)

### 12.3 Response Criteria

#### 12.3.1 Target lesions and target Lymph Nodes

- Measurable lesions (as defined in Section 12.2.1) up to a maximum of 5 lesions, representative of all involved organs, should be identified as “Target Lesions” and recorded and measured at baseline. These lesions can be non-nodal or nodal (as defined in 12.2.1), where no more than 2 lesions are from the same organ and no more than 2 malignant nodal lesions are selected.

**Note:** If fewer than 5 target lesions and target lymph nodes are identified (as there often will be), there is no reason to perform additional studies beyond those specified in the protocol to discover new lesions.

- Target lesions and target lymph nodes should be selected on the basis of their size, be representative of all involved sites of disease, but in addition should be those that lend themselves to reproducible repeated measurements. It may be the case that, on occasion, the largest lesion (or malignant lymph node) does not lend itself to reproducible measurements in which circumstance the next largest lesion (or malignant lymph node) which can be measured reproducibly should be selected.
- Baseline Sum of Dimensions (BSD): A sum of the longest diameter for all target lesions plus the sum of the short axis of all the target lymph nodes will be calculated and reported as the baseline sum of

dimensions (BSD). The BSD will be used as reference to further characterize any objective tumor response in the measurable dimension of the disease.

- **Post-Baseline Sum of the Dimensions (PBSD):** A sum of the longest diameter for all target lesions plus the sum of the short axis of all the target lymph nodes will be calculated and reported as the post-baseline sum of dimensions (PBSD). If the radiologist is able to provide an actual measure for the target lesion (or target lymph node), that should be recorded, even if it is below 0.5 cm. If the target lesion (or target lymph node) is believed to be present and is faintly seen but too small to measure, a default value of 0.5 cm should be assigned. If it is the opinion of the radiologist that the target lesion or target lymph node has likely disappeared, the measurement should be recorded as 0 cm.
- The minimum sum of the dimensions (MSD) is the minimum of the BSD and the PBSD.

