#### 12.3.2.2 Definitions

- Complete Response (CR):** All of the following must be true:
- Disappearance of all target lesions.
  - Each target lymph node must have reduction in short axis to <1.0 cm.
- Partial Response (PR):** At least a 30% decrease in PBSD (sum of the longest diameter for all target lesions plus the sum of the short axis of all the target lymph nodes at current evaluation) taking as reference the BSD (*see* Section 12.3.1).
- Progression (PD):** At least one of the following must be true:
- At least one new malignant lesion, which also includes any lymph node that was normal at baseline (< 1.0 cm short axis) and increased to  $\geq$  1.0 cm short axis during follow-up.

- b. At least a 20% increase in PBSD (sum of the longest diameter for all target lesions plus the sum of the short axis of all the target lymph nodes at current evaluation) taking as reference the MSD (Section 12.31). In addition, the PBSD must also demonstrate an absolute increase of at least 0.5 cm from the MSD.
- c. See Section 12.2.4 for details in regards to the requirements for PD via FDG-PET imaging.

Stable Disease (SD): Neither sufficient shrinkage to qualify for PR, nor sufficient increase to qualify for PD taking as reference the MSD

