### 12.3.3 Non-target lesions and Non-Target Lymph Nodes:

Non-measurable sites of disease (Section 12.2.2) are classified as non-target lesions or non-target lymph nodes and should also be recorded at baseline. These lesions and lymph nodes should be followed in accordance with 12.3.2.1.

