### 17.1 Assessing the impact of adding fulvestrant to alisertib

#### 17.1.1 Primary Endpoint

The primary endpoint is tumor response rate with initial treatment. That is,

- Arm 1: Tumor response rate is defined as 100% times the number of patients who meet the criteria for CR or PR (using RECIST criteria version 1.1) on 2 consecutive evaluations approximately 8 weeks apart during treatment with alisertib monotherapy divided by the number of patients who started alisertib monotherapy.
- Arm 2: Tumor response rate is defined as 100% times the number of patients who meet the criteria for CR or PR (using RECIST criteria version 1.1) on 2 consecutive evaluations approximately 8 weeks apart

during treatment with combination of alisertib and fulvestrant divided by the number of patients who started treatment with the combination of alisertib and fulvestrant.

The study will test the hypothesis that the addition of fulvestrant to alisertib will increase the tumor response rate over that of alisertib alone by at least 20%.

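### As worded, the target-lesion progression rule compares each scan only with baseline, never with the smallest earlier sum; the definition of MSD should be corrected

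*Combined protocol and SAP*

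**What the plan says.** Section 12.3.1 defines a baseline sum (BSD), a post-baseline sum (PBSD) and a minimum sum: "The minimum sum of the dimensions (MSD) is the minimum of the BSD and the PBSD".

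Section 12.3.2.2 then uses two references:
- PR is judged against baseline: "At least a 30% decrease in PBSD", with BSD as reference.
- PD by size is judged against the MSD: "At least a 20% increase in PBSD", and "the PBSD must also demonstrate an absolute increase of at least 0.5 cm from the MSD". The sum being tested is "sum of the longest diameter for all target lesions plus the sum of the short axis of all the target lymph nodes at current evaluation".

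The text names no earlier post-baseline scan as the reference and does not say which status applies if PR and PD are both met. The cross-reference in the PD rule is misprinted: "the short axis of all the target lymph nodes at current evaluation) taking as reference the MSD (Section 12.31".

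Section 17.1.1 counts a response when CR or PR is met "on 2 consecutive evaluations approximately 8 weeks apart". Sections 12 and 17.1.1 name RECIST version 1.1 as the standard.

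Section 12.3.1 limits targets to five lesions, with at most two per organ and at most two nodal. For the rest, Section 12.3.3 says: "Non-measurable sites of disease (Section 12.2.2) are classified as non-target lesions or non-target lymph nodes".

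**The concern.** A minimum sum used as the reference for progression ought to be the smallest sum reached so far, so that regrowth after shrinkage is recognised. As worded it is the smaller of baseline and the scan under test. A shrunken tumour that is growing again then cannot progress by size until it has passed its original size by a fifth.

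The PD call feeds several results. At the primary endpoint, a second scan that shows regrowth can still serve as the confirming PR. PFS, duration of response and clinical benefit (Section 17.1.2) use the PD date or the absence of PD, and crossover in Arm 1 opens at progression (Section 6.1.2).

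There is a related gap. A measurable lesion left out because the target limit is reached is not a target, and it is not a non-measurable site either. Read literally, its growth meets no PD criterion and its persistence does not prevent CR.

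**Working it through.** **The plan's own design figure.** Section 17.2 gives 45 per arm, one-sided alpha 0.15, 85% power for 20% against 40%, a stop at 28 per arm if the difference is one or fewer, and rejection at a difference of at least 4. Exact binomial calculation (continue at 2 or more, reject at 4 or more) gives power 0.850 and alpha 0.147. The design reproduces; the point below does not alter it.

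**The rule as written.** Let C be the current sum and B the baseline sum.
- If C < B, then MSD = min(B, C) = C. The increase is C − C = 0, so PD by size is impossible.
- If C ≥ B, then MSD = B. PD needs C ≥ 1.2B and C ≥ B + 0.5 cm.

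The smallest earlier sum drops out. For B = 10 cm, PD by size starts at 12 cm.

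**Examples** (sums in cm, one scan about every 8 weeks).

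| Sums, baseline first | As written | Against smallest earlier sum, PD taking precedence |
|---|---|---|
| 10, 4.5, 6.0 | PR, PR: confirmed | PR, PD: not confirmed |
| 10, 5, 7, 9, 11, 12 | PR, PR, SD, SD, PD | PR, PD at scan 2 |
| 10, 6, 7, 8 | PR, PR, SD: confirmed | PR, PR, PD: confirmed |

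First row: 6.0/4.5 = 1.33 and 6.0 − 4.5 = 1.5 cm, so both PD thresholds are met against the smallest earlier sum. As written, 6.0/min(10.0, 6.0) = 1.00. The sum is also 40% below baseline, so it meets PR. In the second row PD comes at scan 5 instead of scan 2, about 3 × 8 = 24 weeks later. In the third row 7/6 = 1.17 at scan 2, so the response is confirmed either way and only the PD date differs.

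**When a confirmation is at stake.** The scan right after the first PR must show a rise of at least 20% and 0.5 cm, yet stay at or below 0.70B. The first PR sum must therefore be at or below both 0.70/1.20 = 58.3% of baseline and 70% of baseline minus 0.5 cm. The first limit binds from B = 0.5/(0.70 − 0.583), about 4.3 cm. Below that the second binds: 0.70 − 0.5/3 = 53% at 3 cm and 0.70 − 0.5/2 = 45% at 2 cm.

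**Delay in PD by size (illustration).** The documents give no shrinkage or regrowth rates. Assume S(t) = B(exp(−dt) + exp(gt) − 1), B = 10 cm, scans every 8 weeks, d from 0.08 to 0.20 and g from 0.015 to 0.04 per week, on a 61 × 51 grid. The delay runs from 0 to 32 weeks. For instance, d = 0.20 with g = 0.015 gives PD at week 24 against the smallest earlier sum and week 56 as written; d = 0.08 with g = 0.03 gives week 24 under both. Confirmed-response status changes in about 9% of grid points (14% if the rates are taken as weekly percentages). These are shares of a grid, not of patients. A cruder assumption, a smallest sum at 40–70% of a 10 cm baseline and regrowth of 20–40% per 8 weeks, gives 8 to 48 weeks. The figure depends heavily on what is assumed.

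**The case against.** The best defence is that the literal reading is not the intended one. Section 12.3.1 defines PBSD without limiting it to one scan. The mention of the current evaluation in Section 12.3.2.2 may serve only to say which PBSD is being tested. On the literal reading MSD never changes a result that BSD would give, so the term would be pointless; as a running minimum it has a purpose. RECIST 1.1 is named twice, and sites may already use the smallest earlier sum.

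This stands as evidence of intent, and it rules out an inference a reader might draw: that patients were in fact misclassified. Nothing in the documents shows that. It does not cure the wording. The operational definition is explicit, and a site or programmer who follows it gets a different status from one who follows the evident intent. Even as a running minimum, the 6.0 cm scan above meets both PR and PD, and the text does not say which prevails.

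The other routes to PD also remain: new lesions, unequivocal non-target progression, the FDG-PET rules (Section 12.2.4) and symptomatic deterioration (Section 12.3.4). Only the target-sum route is weakened, and the delay model ignores the rest.

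**Conclusion.** The wording is wrong as it stands and should be fixed. It is a drafting defect that conflicts with the plan's own apparent purpose, not a flaw in sample size, alpha or power.

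For the primary endpoint the effect is probably small. It needs a deep first response followed by regrowth at the very next scan, to a sum still at or below 70% of baseline. For PFS, duration of response, clinical benefit and the crossover date it may be larger, with the 0 to 32 week delay as an illustration resting on assumed rates. How many patients are affected is unknown.

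Three stronger readings are tempting but not supported:
- That every deep responder who later regrows is falsely confirmed. If the second scan shows PR without PD, the response is confirmed under either reading. PR status also lasts only up to 70% of baseline; from there to the PD threshold the status is SD.
- That one or two such patients would decide the trial. Section 17.2 requires at least 4 more responses on the combination than on alisertib alone, not 4 responses. Both arms share the rule, so errors partly cancel, and the documents give no reason to expect an imbalance. A net shift of one patient matters only if the difference lies on the boundary.
- That PD is always called late. The model includes cases with no delay.

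The gap for unselected measurable lesions follows from the text, but no size can be put on it.

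**What to change.** 1. In Section 12.3.1, define MSD as *the smallest sum recorded at baseline or at any evaluation before the current one*.
2. In Section 12.3.2.2, state that an evaluation meeting both PR and PD is PD, and correct the cross-reference to Section 12.3.1.
3. In Section 12.3.3, state that the non-target set holds all other sites of disease, including measurable lesions and nodes not selected as targets.
4. Derive objective status, response confirmation and PD dates from the recorded RECIST measurements with these definitions.

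The cost is a wording change and one programming rule. RECIST measurements are already collected at each evaluation (Section 14.1.3), and the sample size does not change. The documents do not say whether unselected measurable lesions were recorded, so item 3 may need a check of the forms. The response rate and PFS may come out slightly less favourable.
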